9.4. Handling of Adverse Events

If an AE occurs, appropriate diagnostic and therapeutic measures are to be taken and the investigational product and/or non-investigational product including – but not limited to – rescue medication has to be discontinued if appropriate. Follow-up evaluations of the patient are to be performed until the patient recovers or until the clinical investigator considers the situation to be no longer clinically significant.

Investigators monitor and register all AEs on the *AE form* of the eCRF at each visit. For any AE a specific diagnosis rather than signs or symptoms have to be given in the eCRF. In absence of a specific diagnosis, an individual *AE form* has to be filled in for each, sign or symptom to allow proper MedDRA coding.

Persistent AEs will be entered once in the eCRF until they are resolved or if a new event has to be documented due to deterioration. These AEs will be carefully monitored; further details of monitoring of persistent AEs will be provided in the Data Handling Manual/ Data Validation Plan. If an AE is still not resolved at the end of the study for the individual patient, this will be documented as ongoing at study completion.

For recurrent AEs, i.e. AEs of the same nature, but with a different date of onset, an individual *AE form* has to be completed for each of them.

AEs occurring after the termination of the study for the individual patient and/or of the study in total are to be reported to Biologische Heilmittel Heel GmbH even after the clinical trial has been completed if, in the judgement of the investigator, there is an association between the event and the previous use of the product under investigation.

9.5. Reporting of Serious Adverse Events

If the AE is classified as serious, the clinical investigator has to complete and also sign the SAE module in the eCRF. It is the responsibility of the investigator to send the SAE report out of the eCRF to the Drug Safety Department and Study Team of the designated CRO within **24 hours** after being aware of it, and print the report out of the eCRF and file it in the Investigator Site File. At the earliest possible date, the *SAE report form* has to be followed by a detailed report and any documentation that may become available, e.g. hospital records, autopsy reports, and/or other pertinent documents.

All the above documents in addition to the SAE report will be sent by fax to the Drug Safety Department of the designated CRO within 24 hours (see fax number below) and the original documents will be filed in the Investigator Site File. Personal data of the patient should be deleted or blackened, the 7-digit patient number (formerly named ‘E-code’) and study code (C1502) to be used for patient identification.

For reporting SAEs in the event of technical failure of eCRF, a paper form of *SAE Report* need to be completed and faxed within 24 hours using the following contact:

AMS Safety Department (CRO)

[contact]

At the earliest possible date, the SAE report form has to be completed in the eCRF and procedures described in the first paragraph should be followed. A detailed follow-up report and any documentation that may be available, e.g. hospital case records, autopsy reports, and/or other pertinent documents will be sent via fax.

The primary person responsible for Safety at the Pharmacovigilance Department of Biologische Heilmittel Heel GmbH is:

[name]
Biologische Heilmittel Heel GmbH
[name]
[name], Germany
[contact]
[contact]
Email: [contact]

Availability in emergency patient safety situation (24 hours in 7 days/week)
[contact]

The Qualified Person for Pharmacovigilance (QPPV) at Biologische Heilmittel Heel GmbH is:

[name]
Biologische Heilmittel Heel GmbH
[name]
[name], Germany
[contact]
[contact]

Heel complies with applicable regulatory requirement(s) related to the reporting of SAEs and SUSARs to the Competent Regulatory Authority, ECs and investigators. In addition, Heel or designated CRO will prepare an annual Development Safety Update Report (DSUR) according to regulatory requirements.

9.6. Pregnancy

Females who are pregnant or breast-feeding are not allowed to participate in this clinical trial. Pregnancy test will be performed for woman of childbearing potential before first study drug administration to exclude pregnancy. Woman is considered of childbearing potential, i.e. fertile, following menarche and until becoming post-menopausal unless permanently sterile. Permanent sterilisation methods include hysterectomy, bilateral salpingectomy and bilateral oophorectomy.

A postmenopausal state is defined as no menses for 12 months without an alternative medical cause. A high follicle stimulating hormone (FSH) level in the postmenopausal range may be used to confirm a post-menopausal state in women not using hormonal contraception or hormonal replacement therapy. However, in the absence of 12 months of amenorrhea, a single FSH measurement is insufficient.

In the Summary of Product Characteristics for Diclofenac Heumann Gel (HEUMANN PHARMA GMBH & CO. GENERICA KG, N., 2013), administration of Diclofenac Heumann Gel is under 4.6 only recommended during the first and second trimester of pregnancy if absolutely required.

Females of childbearing potential must agree to maintain highly effective birth control throughout the study. Such methods include:

- combined (oestrogen and progestogen containing) hormonal contraception associated with inhibition of ovulation:
 - oral
 - intravaginal
 - transdermal
- progestogen-only hormonal contraception associated with inhibition of ovulation:
 - oral
 - injectable
 - implantable¹
- intrauterine device (IUD) ¹,
- intrauterine hormone-releasing system (IUS) ¹
- bilateral tubal occlusion¹
- vasectomised partner^{1,2}
- sexual abstinence³.

¹ Contraception methods that in the context of this guidance are considered to have low user dependency.

² Vasectomised partner is a highly effective birth control method provided that partner is the sole sexual partner of the woman of child bearing potential trial participant and that the vasectomised partner has received medical assessment of the surgical success.

³ In the context of the guidance sexual abstinence is considered a highly effective method only if defined as refraining from heterosexual intercourse during the entire period of risk associated with the study treatments. The reliability of sexual abstinence needs to be evaluated in relation to the duration of the clinical trial and the preferred and usual lifestyle of the subject.

All pregnancies observed during the course of the study and their outcomes should be reported to CRO and/or the Sponsor. If a patient becomes pregnant the investigational product should be discontinued immediately and the patient should be withdrawn from the study. The Investigator or other site personnel informs the CRO and/or the Sponsor within 24 hours of when he or she becomes aware of the pregnancy.

Pregnancy Report Form should be used for reporting and to be sent via fax to:

AMS Safety Department (CRO)

[contact]

The designated CRO and/or Sponsor representative works with the Investigator to ensure that all relevant information is provided within 24 hours in case of SAE and within 30 days for pregnancies without any complications.

Pregnancy itself is not considered as AE, but any complications e.g. congenital abnormalities, birth defects, and spontaneous miscarriages should be handled and reported as SAEs.

The outcome of pregnancy should be followed up, documented and reported to CRO and/or Sponsor within the same timeframe as described above.

10. Data Quality Assurance

10.1. Data Collection, Monitoring, and Auditing

Detailed procedures will be separately provided in the data management, monitoring, and quality plans.

10.1.1. Data Collection

All clinical study data of randomized patients are to be recorded in the eCRF/ Clinical Data Management System Clincase[®].

All patient data have to be reported in the eCRFs in a pseudonymous fashion. Patients are identified by a unique 7-digit patient identification number (patient number, in previous protocol versions referred to as 'E-code') generated in the eCRF.

The investigator will be responsible for the completeness, accuracy, and legibility of the information in the eCRF and other study documents. For documents other than eCRF, only ballpoint pen is to be used and any change of data is to be done by striking out the incorrect data with a single line and dating and initialling the changes made.

The study monitors then have to check the eCRF entries against the source documents (100% source data verification) for accuracy and validity as per the Monitoring Plan as applicable.

The patient diary will remain as source at the site and will only be reviewed by the monitors but not collected. The diary data will be transcribed into appropriate sections of the eCRF by site personnel. Source data will include FAAM-ADL questionnaires, VAS recordings, medical records, diary data and drug accountability of IMP tubes and rescue medication blisters.

Upon completion of the examination timely completion of the eCRF (within 24 hours for Visit 1, all other patient visits within 72 hours) is expected from the site personnel to ensure quality of data and to have oversight on patient safety. Once eCRF entries for a patient (visit) are completed, they will be available for review by the monitor and the designated CRO Clinical Data Management department. Completed eCRFs will be reviewed remotely for completeness, logical discrepancies and clinical consistency. The monitor will ensure that all data queries and subsequent amendments in the eCRF documentation are made according to GCP guidelines.

Electronic copies of the site-specific eCRFs including audit trails have to be archived by the investigator together with the study documents, source data, and laboratory records (if applicable) for the time required by relevant guidelines and national regulations. Any evaluations documented on paper will be entered into the eCRF. The original entries on paper documents, including those completed by the patient, will be considered source data.

10.1.2. Confidentiality/ Property

Adequate records have to be maintained for the study, including patient medical records, eCRFs, laboratory reports, worksheets, nursing notes, signed informed consent forms, product forms, SAE paper forms (to be used in case the eCRF is not available), and

information regarding patient discontinuation and reasons for discontinuation. The confidentiality of each record with patient identification (unique 7-digit patient number) is to be guaranteed by the clinical investigator.

This study protocol and other study documents contain trade secrets and commercial information that is privileged and confidential. Such information is not to be disclosed unless required by laws or regulations. The investigator agrees to use this information only in conducting this study and is not allowed to use it for any other purposes without written consent from the Sponsor. Results obtained from this study are the property of the Sponsor.

10.1.3. Retention of Records

The investigator agrees to retain electronic copies of the eCRFs of his/her trial patients, the Investigator Site File and other relevant study-related documents (e.g. the protocol and any protocol amendments, the IMP reference safety information, CA and IEC approval, signed patient informed consent forms, and source documents for each patient in the study [e.g. all study-related demographic and medical information, medication disposal, patient diaries and patient reported outcomes]) in a secure place as long as needed to comply with national and international regulations (generally for 15 years). These records have to be made available for audits or inspections upon reasonable request by a representative of the Sponsor or regulatory authorities. Before the investigator destroys any of the above-mentioned documents (only after 15 years or as regulated), he informs Heel in writing.

In case the investigator retires, relocates, or for any other reason withdraws from the responsibility for maintaining records for the period of time required, custody of the records has to be transferred to any other person who accepts responsibility for the records, e.g. another investigator, or an external archive contracted by the Sponsor. Notice of such transfer has to be given in writing to the sponsor.

10.1.4. Routine Monitoring

To ensure compliance a site visit will be held prior to initiation of patient recruitment (Site Initiation Visit). The protocol, eCRFs, study treatment supplies, handling of study medication, the role of the team member responsible for study medication and other study procedures will be explained in detail.

A monitor assigned by the designated CRO will conduct regular site visits for the purpose of study monitoring.

The purpose of the regular monitoring visits is to ensure that the rights and wellbeing of human patients are protected; that study data are accurate, complete, and verifiable with

source data; and that the study is conducted in compliance with the protocol, GCP, and the applicable regulatory requirements.

The investigator must agree to allow the study monitor and authorised representatives of the designated CRO and/or Heel to inspect all eCRFs and corresponding source documents (e.g. original medical records, patient records and other relevant records); to allow access to the clinical supplies, dispensing, and storage areas; and to agree to assist with their activities, if requested. The investigator should provide adequate time and facilities for monitoring visits.

The monitor will query any missing or spurious data with the investigator, which should be resolved in a timely manner. A monitoring log will be maintained to record each monitor visit, the reason for the visit, the monitor's signature, and the investigator's or designee's confirmation signature.

10.1.5. Site Audits

Biologische Heilmittel Heel GmbH or its designee may carry out an audit at any time. Investigators will be given adequate notice before the audit occurs. The purpose of an audit is to confirm that the study is conducted as per protocol, GCP and applicable regulatory requirements, that the rights and well-being of the patients enrolled have been protected, and that the data relevant for the evaluation of the investigational product have been captured, processed and reported in compliance with the planned arrangements. The investigator will permit direct access to all study documents, drug accountability records, medical records, and source data.

Regulatory authorities may perform an inspection of the study, even up to several years after its completion. If an inspection is announced, Heel must be informed immediately.

10.2. Database Management and Quality Control

The designated CRO will be responsible for the activities associated with the data management of this study, including the production of an eCRF, setting up a relevant database, along with appropriate validation of data and resolution of queries. All data will be entered into an eCRF. Automated and manual checks will be made against the data to ensure completeness and consistency. Resolution of queries will be implemented in the database.

AEs will be standardised for terminology and classification, using Medical Dictionary for Regulatory Activities (MedDRA) Dictionary (the latest available version at study start will be used for the entire duration of the study).

Concomitant medical conditions and Medical History terms will be standardised for terminology and classification, using Medical Dictionary for Regulatory Activities

(MedDRA) Dictionary (the latest available version at study start will be used for the entire duration of the study).

Concomitant drugs will be standardised for terminology and classification using WHO Drug Dictionary.

11. Statistical Methods and Determination of Sample Size

11.1. Statistical and Analytical Plans

Clinical efficacy will be assessed as superiority of Traumed[®] gel versus placebo and as non-inferiority of Traumed[®] gel compared to diclofenac gel regarding the primary efficacy parameter indicated below.

Clinical safety will be addressed by assessing AEs, physical examinations and vital signs results in a descriptive manner.

All items of the eCRF will be presented in individual patient data listings and in appropriate summary tables. Standard descriptive summary statistics will be calculated for continuous variables (i.e. arithmetic mean, standard deviation, minimum value, median, maximum value, number of non-missing values). Categorical data will be presented in frequency tables using counts and percentages. Individual patient data listings will be presented per parameter and will be sorted appropriately. Summary tables will be displayed by treatment group and visit (if applicable). Where appropriate the presentation will include changes from baseline and shift tables.

Further details of the planned analyses will be given in the statistical analysis plan (SAP), which will be developed by the designated biostatistician for approval by Heel GmbH well in advance before unblinding the study.

11.1.1. Data Sets to be Analysed

Analyses will be based on the Safety Analysis, Full Analysis, and the Per-Protocol analysis sets. The definitions of the analysis sets follow those given in the ICH E9 guideline (CMP/ICH/363/96).

Safety Analysis Set: Randomised patients who receive at least one dose of investigational medication will form the Safety Analysis Set. The Safety Analysis Set will be used for all analyses of safety, tolerability, and background characteristics. For this set, the exposure to IMP will be also analysed.

Full Analysis Set (FAS): The Full Analysis Set is a subset of the Safety Analysis Set consisting of all patients with acute unilateral Grade 1 or Grade 2 sprain of the lateral

ankle, for whom both baseline and Day 4 VAS values of pain are available. The Full Analysis Set will be used for the Intent-to-Treat (ITT) analysis.

Per-Protocol (PP) Set: Patients in the Full Analysis Set without major protocol deviations will form the PP Set. The PP Set will be used for the per-protocol analysis of the efficacy parameters. The same efficacy evaluations as in the FAS are planned. Relevant differences between the FAS and PPS will be evaluated in the clinical trial report.

Protocol deviations will be collected during the entire study and will be classified as minor or major at the Blind Data Review Meeting (BDRM). Protocol deviations that may affect the efficacy outcome of participants will be classified as major. The decision about major protocol deviations and assignments to populations will be documented in the BDRM meeting minutes.

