11.1.4. Accounting for Missing Data

Missing data represent a potential source of bias in a clinical trial. For the clinical trial at hand two general approaches are pursued:

- Avoidance of drop-outs
- Using sensitivity analyses in order to demonstrate the robustness of the results of the first line analyses.

The pre-planned analysis procedures are as follows:

1. Last Observation Carried Forward [LOCF] (Applied to all Efficacy Analyses)

A LOCF analysis (Last Observation Carried Forward) will be performed as first line analysis. LOCF will be applied for missing values regardless of the reason for discontinuation.

2. Last Percentile Carried Forward [LPCF] (Applied as Sensitivity Analysis to the First Line Efficacy Analyses)

The LPCF method carries forward the change information, using the percentile value with back transformation to raw scale, instead of last value carried forward. This approach was recently developed and recommended by O'Brien, Zhang and Bailey in 2005 (O'Brien et al. 2005). The results of this method are well comparable to the mixed-effect models for repeated measures (MMRM), without making the corresponding parametric assumptions. According to their simulation study the calculated estimators should be negligibly biased by missing data.

Additional sensitivity analyses resulting from the blind review of the data and further technical details will be provided in the final statistical analysis plan.

The frequency and type of missing values will be documented in the clinical study report.

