11.4. Determination of Sample Size

Estimation of sample size is based on the primary efficacy variable. A two-sided test of equality of the study drug (Traumed[®] gel) and the comparator (placebo) at level 0.05 based on an expected raw scale treatment difference of AUC 25 [mm x days] and a common standard deviation of AUC 75 [mm x days] for the response variables (re-expressed for nonparametric evaluation in terms of the Mann-Whitney statistic as $MW = 0.6$ (see section 11.1.3), achieves a power of at least 90% for parametric first line analysis as well as for second line nonparametric analysis if the sample size is set to 291 patients for the Traumed[®] gel group and to 146 patients for the placebo group.

Due to an additional safety requirement that AEs with incidence level of 1% for Traumed[®] gel are found during the study with probability 95%, 299 patients for the Traumed[®] gel group are required. Assuming a drop-out rate from the Safety Analysis Set of about 4% an amount of 312 randomized patients in the Traumed[®] gel group is needed. With an allocation ratio of 2:1:1 (Traumed[®] gel : diclofenac gel : placebo) 156 patients are obtained in the diclofenac gel and placebo group each, that is, a total of 624 patients with acute unilateral Grade 1 or Grade 2 sprain of the lateral ankle.

In order to ensure the pre-defined power of the trial for the trial objectives including the confirmatory test for non-inferiority (Traumed[®] gel compared to diclofenac gel), which is based on the Per-Protocol Analysis Set (PP), a sample size enhancement is introduced for compensation of:

- cases for whom maintenance of blinding procedures may have been compromised and, thus, are representing a major protocol violation (exclusion from PP analysis).

For compensation, the final sample size will be enhanced to 202 patients for the diclofenac and Placebo group each, and to 404 patients for the Traumed[®] gel group resulting in a new total of 808 patients. *(revised per Amendment to protocol version 3.0)*

12. Study Report and Publication Policy

An integrated study report in accordance with the ICH Harmonized Tripartite Guideline (E3) (Structure and content of clinical study reports) will be developed.

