9.5.1.2 Additional Operationalizations

- The imputation by means of Last Observation Carried Forward [LOCF] will be applied to all first line analyses (confirmatory and exploratory) with the exception of the secondary efficacy variables no. 7 and 8 (see section 9.3.2). Imputation of missing values is performed using the last existing follow-up value. The imputation by means of Last Percentile Carried Forward [LPCF] will be omitted due to the marginal number of missing efficacy values.
- The number of non-missing values will be documented in the Clinical Trial Report for all variables and evaluations (valid number). The frequency and type of missing values will be documented in the Clinical Trial Report for the primary efficacy variable (area under the curve, AUC) of pain on passive movement in Visual Analog Scale (VAS) from baseline to Day 4.
- The standard ensemble of classic and robust summarizing statistics (see section 9.1) will be provided for the pre-specified imputation as well as for *data as available*, i.e. without imputation.

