9.7.1.2 Additional Operationalizations

- In order to preserve validity and integrity of the trial, all confirmatory and secondary analyses will be based on the group of non-issue patients (for details see section 8 Changes to the Protocol). As stated in the 'Amendment Summary Document for Substantial Protocol Changes', the sample size was proactively enhanced to ensure planned power and validity for evaluating the pre-defined trial objectives also in case that only non-compromised cases allow valid and unbiased conclusions. Results of issue patients will be provided separately in the Appendix of the Clinical Trial Report (CTR).
- FAS: VAS availability at Day 4 is referring to LOCF (primary analysis).
- PP: premature discontinuations due to "lack of efficacy", "adverse event", or
 "lack of efficacy" and "adverse event" (i.e. drug-related premature
 discontinuations) will not be excluded from the PP analysis, regardless of any
 existing protocol deviation. Benchmarks for "Major Protocol Deviation" (final
 BDRM decisions):
 - Grade 3 determination after Visit 3
 - VASPM V1 < 50
 - Missing VASPM at V1 or V3 (Related to ,Data as Available')
 - Visit 2 \leftrightarrow Day 2 (Protocol Day 2)
 - Visit 3 < Day 4 or > Day 5 (Protocol Day 4 + 1 Day)
 - Visit $4 < \text{Day } 6 \text{ or } > \text{Day } 9 \text{ (Protocol Day } 7 \pm 1 \text{ day)}$
 - Compliance < 80% at V3 or V4
 - Premature Discontinuation (not drug-related)
 - The analysis populations (Safety, FAS, and PP) are listed individually in the Appendix of the final Statistical Analysis Plan.

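### Dosed patients with a baseline pain score but no later score stay outside the FAS, which is labelled ITT, and outside every planned efficacy analysis

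*Protocol*

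**What the plan says.** Protocol 11.1.1 builds the FAS from the Safety Analysis Set, keeping Grade 1 or 2 patients "for whom both baseline and Day 4 VAS values of pain are available", and assigns this set to the ITT analysis. Protocol 11.1.3 makes it the primary set for superiority over placebo. On missing data, protocol 11.1.4 states: "LOCF will be applied for missing values regardless of the reason for discontinuation".

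SAP 9.7.1.1 repeats the protocol definition, and SAP 9.7.1.2 then interprets it: "FAS: VAS availability at Day 4 is referring to LOCF (primary analysis"). SAP 9.5.1.2 describes the mechanism: "Imputation of missing values is performed using the last existing follow-up value". The same section drops LPCF, the only missing-data sensitivity analysis the protocol names, because few efficacy values are missing.

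SAP 13.3 plans efficacy displays for the FAS and PP sets only, and the PP set is a subset of the FAS. Under SAP 9.3.1.2 the Day 4 superiority test (hypothesis 1) gates the three tests that follow, including Day 7 superiority (hypothesis 3).

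**The concern.** An intent-to-treat set should not depend on what happens after randomisation. Whether a Day 4 score exists is such an event. On the protocol wording alone, the entry rule and the LOCF rule conflict for the primary endpoint: anyone whose Day 4 score LOCF would supply has already been excluded.

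The SAP's reading lets in patients with some later score. One group remains outside: patients dosed on Day 1 who have a baseline VAS and nothing after it. Protocol 5.3.4 lists loss to follow-up and withdrawal of consent among the reasons for leaving the study, with no further assessments afterwards. If such early leavers differ between arms, both in number and in pain course, the superiority comparison carries a selection bias that no planned analysis would reveal.

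**Working it through.** **1. Who enters the set.** Take dosed, non-issue patients with Grade 1 or 2 sprain and a baseline VAS.

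| VAS after baseline | Protocol FAS, read literally | FAS under the SAP |
|---|---|---|
| Day 4 observed | in | in |
| Day 2 or discontinuation-visit score, no Day 4 score | out | in, by LOCF |
| none | out | out: no follow-up score to carry |

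The third row is the residual gap. Such patients count for safety but appear in neither efficacy set.

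**2. The plan's own sample size.** The inputs in protocol 11.4 are a difference of 25 mm x days, an SD of 75 mm x days and a two-sided 5% level. For 291 Traumed and 146 placebo patients, its claim is that the test "achieves a power of at least 90% for parametric first line analysis".

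- Placebo n at 2:1 = (1 + 1/2) x [75 x (1.960 + 1.2816) / 25]² = 141.85, so 142, with 284 on Traumed.
- At 291/146, SE = 75 x √(1/291 + 1/146) = 7.61, and power = Φ(25/7.61 − 1.96) = 90.8% (90.6% by noncentral t).

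The stated figure is reproduced.

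**3. Is power at stake?** The enlarged total less the issue patients is 808 − 184 = 624. Assume that these split 312:156:156, as in the initial plan.

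| Assumed loss from each arm | Power (Traumed vs placebo) |
|---|---|
| 0% | 92.5% |
| 2% | 92.0% |
| 4% | 91.5% |
| 6% | 90.9% |
| 8% | 90.3% |
| 10% | 89.7% |

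Power stays above 90% until close to 10% is lost, so this is not a power problem.

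**4. Size of a possible bias.** Suppose a fraction m of one arm is lost, and the lost patients' mean AUC is D worse than that of retained patients in that arm. The arm's full mean is (1 − m) x retained + m x lost, so the retained mean differs from it by m x D. Neither m nor D is in the documents. As an assumed scale, take m = 1% and D = 0.5 to 1 SD, that is 37.5 to 75 mm x days:

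- Shift: 0.01 x 37.5 = 0.375 and 0.01 x 75 = 0.75 mm x days, or 1.5% to 3% of the 25 mm x days effect.
- SE at 312/156 = 75 x √(1/312 + 1/156) = 7.35, so the shift is 0.05 to 0.10 SE.
- With a 0.10 SE shift and no true effect, the two-sided rejection rate goes from 5% to about 5.1%.

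**5. Direction.** A higher AUC means more pain. Losing worse patients from placebo flatters placebo and works against Traumed. Losing them from Traumed works in its favour. Nothing in the documents shows which applies.

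**The case against.** The case against is substantial, and most of it stands.

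- **The SAP has largely resolved the conflict.** Its reading of availability sits openly beside the protocol definition, in a plan to be signed before unblinding. Whether it should also appear in SAP section 8 is only a question of placement.
- **The residual group is narrow.** Visit 2 is the day after baseline. Patients who stop treatment, including for lack of efficacy, should have a discontinuation visit (protocol 5.3.3), and that visit records VAS (7.2.5). Essentially only those who vanish or withdraw before any further visit remain.
- **The count may be known.** SAP 9.7.1.2 says that set membership is listed individually in the appendix. Those pages were not available here, and the number could be zero. Disposition and analysis-set tables are also planned.

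A reader might infer that the protocol rule cancels LOCF altogether. It does not: even read literally, LOCF can still fill a missing Day 2, Day 7 or Final Visit score. Only the Day 4 score is beyond its reach.

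A reader might also apply the 4% drop-out in protocol 11.4 to this loss and obtain a larger bias. That figure covers the step from randomised patients to the Safety Analysis Set (299 / 0.96 = 311.5, so 312). It does not cover the step from the Safety Analysis Set to the FAS, and cannot be used here.

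What the objections leave untouched is that a table of exclusions puts nobody into an analysis, and that the wording of SAP 9.5.1.2 gives baseline-only patients no value.

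**Conclusion.** The point holds in a limited form and is minor. The set for the gating superiority test, presented as intent-to-treat, still selects on a post-randomisation event: having at least one VAS after baseline. The affected group is probably very small, given the SAP's remark that missing values are marginal in number.

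The shift of about 0.4 to 0.75 mm x days rests on an assumed 1% loss confined to one arm and an assumed difference of 0.5 to 1 SD. It indicates scale and is not an estimate. The documents do not support inferring a bias in favour of Traumed, a material inflation of the error rate, or a loss of power. The exclusions for Grade 3 regrading and for compromised blinding are separate rules and are not part of this point.

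**What to change.** - **SAP 9.7.1.2:** replace the Day 4 availability condition with at least one dose and a baseline VAS on passive movement, keeping the Grade 1 or 2 condition.
- **SAP 9.5.1.2:** let LOCF carry the baseline score forward when no follow-up score exists. State the nominal time given to an imputed Day 4 score, because AUC uses actual measurement times and neither document says what an imputed score receives.
- **Sensitivity analysis:** for hypotheses 1 and 3, vary the values imputed for these patients, including values worse than those of retained patients in the same arm. Imputing from baseline and arm alone would add little, because the ANCOVA already assumes that leavers resemble retained patients with the same baseline and arm.
- **Reporting:** give the number of these patients by arm.
- **Knock-on check:** the PP set draws on the FAS, and SAP 9.7.1.2 keeps drug-related discontinuations in PP regardless of deviations. State whether such a patient without any follow-up score would then enter PP.

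The cost is a few lines of text and a little programming, with no new data: the inclusion criteria already require a baseline passive-movement score. The downside is a few fully imputed values and possibly a slightly less favourable estimate. If the SAP has already been signed, its section 11 requires major later changes to be reported in the Clinical Trial Report with a rationale.
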